1.3 Secondary Objectives

The secondary objectives of the study are:

- 1) To evaluate Progression Free Survival (PFS).
- 2) To evaluate change in pCDC2 after therapy with AZD1775 in paired biopsies
- 3) Evaluate incidence of p53 mutations in tumor tissue and correlate mutational status with response
- 4) To evaluate change in markers for DNA damage (gamma-H2AX, phospho-Histone 3, and caspase 3) after exposure to cisplatin + AZD1775 compared to cisplatin therapy alone in paired biopsy samples
- 5) To evaluate the incidence BRCA1 and BRCA2 mutations, and correlate mutational status with response

- 6) To explore other possible gene mutations that may correlate with response.
- 7) To correlate next generation sequencing of tumors with participant outcomes (ORR and PFS) in DFCI participants only.

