To evaluate the relationship between BRCA status and response, the data will be tabulated and Fisher's exact test will be applied, recognizing that only large differences are detectable if the overall response rate is 30% (78% power to detect response rate of 83% among BRCA+ and 20% among BRCA- assuming 15% of patients are deemed BRCA+ and data are available for all 35 patients).

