'Cystic lesions' thought to represent cystic metastases can be considered as measurable lesions, if they meet the definition of measurability described above. However, if non-cystic lesions are present in the same participant, these are preferred for selection as target lesions.

Target lesions. All measurable lesions up to a maximum of 2 lesions per organ and 5 lesions in total, representative of all involved organs, should be identified as **target lesions** and recorded and measured at baseline. Target lesions should be selected on the basis of their size (lesions with the longest diameter), be representative of all involved organs, but in addition should be those that lend themselves to reproducible repeated measurements. It may be the case that, on occasion, the largest lesion does not lend itself to reproducible measurement in which circumstance the next largest lesion which can be measured reproducibly should be selected. A sum of the diameters (longest for non-nodal lesions, short axis for nodal lesions) for all target lesions will be calculated and reported as the baseline sum diameters. If lymph nodes are to be included in the sum, then only the short axis is added into the sum. The baseline sum diameters will be used as reference to further characterize any objective tumor regression in the measurable dimension of the disease.

Non-target lesions. All other lesions (or sites of disease) including any measurable lesions over and above the 5 target lesions should be identified as **non-target lesions** and should also be recorded at baseline. Measurements of these lesions are not required, but the presence, absence, or in rare cases unequivocal progression of each should be noted throughout follow up.

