11.1.4 Response Criteria

11.1.4.1 Evaluation of Target Lesions

Complete Response (CR): Disappearance of all target lesions. Any pathological lymph nodes (whether target or non-target) must have reduction in short axis to <10 mm.

Partial Response (PR): At least a 30% decrease in the sum of the diameters of target lesions, taking as reference the baseline sum diameters.

Progressive Disease (PD): At least a 20% increase in the sum of the diameters of target lesions, taking as reference the smallest sum on study (this includes the baseline sum if that is the smallest on study). In addition to the relative increase of 20%, the sum must also demonstrate an absolute increase of at least 5 mm. (Note: the appearance of one or more new lesions is also considered progressions).

Stable Disease (SD): Neither sufficient shrinkage to qualify for PR nor sufficient increase to qualify for PD, taking as reference the smallest sum diameters while on study.

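### Fisher's exact test for BRCA status against response is conservative at 5 versus 30 patients; Boschloo's exact test on the same table raises power from 0.788 to 0.844 at the same nominal level

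*Combined protocol and SAP*

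**What the plan says.** Section 1.3 lists as secondary objective 5: "To evaluate the incidence BRCA1 and BRCA2 mutations, and correlate mutational status with response". Section 9.1 gives the analysis: "the data will be tabulated and Fisher's exact test will be applied, recognizing that only large differences are detectable". It supports this with a power statement, "78% power to detect response rate of 83% among BRCA+ and 20% among BRCA"-negative patients, "assuming 15% of patients are deemed BRCA+ and data are available for all 35 patients". No significance level or sidedness is given for this test.

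Section 9.1 also labels all biomarker analyses of blood and tissue as exploratory. The decision on the regimen rests on the two-stage response rule in Section 13.1, not on this test.

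Response is by RECIST 1.1. The partial-response cut in Section 11.1.4.1 is "At least a 30% decrease in the sum of the diameters of target lesions, taking as reference the baseline sum diameters". Section 11.1.4.4 adds non-target lesions, new lesions and confirmation. Of the underlying measurement, Section 11.1.2 says: "The baseline sum diameters will be used as reference to further characterize any objective tumor regression in the measurable dimension of the disease". No analysis of percent change in that sum by BRCA status is planned.

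**The concern.** Only 5 or 6 BRCA-positive patients are expected, so the test should not give away power that the data can supply. Fisher's test conditions on the total number of responders. With one group this small it has few attainable p-values, and much of the nominal 0.05 goes unused. A less conservative exact test exists for the same table.

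What is at stake is the chance that objective 5 gives an answer. The plan's alternative, 83% against 20%, is very large. The only BRCA-specific platinum response rate in the documents is 68%, with carboplatin (Section 2.3). At that rate against 20%, Fisher's test has power of only about one half.

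**Working it through.** **Inputs.** Response rates of 83% and 20%, 15% BRCA-positive, and 35 patients come from Section 9.1. The group sizes are 0.15 × 35 = 5.25, so 5 versus 30, or 6 versus 29 if rounded up. As a check on the rates, 5 × 0.83 + 30 × 0.20 = 10.15, and 10.15/35 = 29%, in line with the 30% overall rate stated there. Two-sided 0.05 is my assumption.

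**Step 1: reproduce the plan's power.** Let X ~ Bin(5, 0.83) be the responders among BRCA-positive patients and Y ~ Bin(30, 0.20) those among BRCA-negative patients. In the direction of the alternative, Fisher's test rejects when X = 5 and Y ≤ 14, X = 4 and Y ≤ 8, X = 3 and Y ≤ 4, or X = 2 and Y ≤ 1. The rejecting tables in the other direction add almost nothing.

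- X = 5: 0.3939 × 0.9998 = 0.3938
- X = 4: 0.4034 × 0.8713 = 0.3515
- X = 3: 0.1652 × 0.2552 = 0.0422
- X = 2: 0.0338 × 0.0105 = 0.0004

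The sum is 0.788, which agrees with the stated 78%. The one-sided test at 0.05 gives the same 0.788. With the 37 patients of Section 13.1, power is 0.795 (5 versus 32) or 0.839 (6 versus 31), so the 35-versus-37 difference hardly matters here.

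**Step 2: true size of Fisher's test.** The probability of rejection was summed over all tables with a common response rate in both groups. At 5 versus 30 it is 0.020 at a common rate of 30%, and at most 0.029 over all common rates.

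**Step 3: Boschloo's test.** Order the tables by two-sided Fisher p-value and take the largest rejection region whose size is at most 0.05 over a grid of 999 common rates. At 5 versus 30 this admits tables with a Fisher p-value up to 0.0665. Its maximum size is 0.043, and the next step would reach 0.051. The cut-offs on Y become 15, 9, 5 and 1 for X = 5, 4, 3 and 2:

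- X = 5: 0.3939 × 0.9999 = 0.3939
- X = 4: 0.4034 × 0.9389 = 0.3788
- X = 3: 0.1652 × 0.4275 = 0.0706
- X = 2: 0.0004, as before

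The sum is 0.844 (0.8436 before rounding of terms). The region contains every table that Fisher's test rejects.

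| Groups | Rates | Fisher | Boschloo |
|---|---|---|---|
| 5 vs 30 | 83% vs 20% | 0.788 | 0.844 |
| 6 vs 29 | 83% vs 20% | 0.849 | 0.891 |
| 5 vs 30 | 68% vs 20% | 0.53 | 0.61 |

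The ordering matters. A two-sided version that doubles the smaller one-sided Boschloo p-value gives only 0.815 (5 versus 30) and 0.861 (6 versus 29).

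**Step 4: rank test on percent change.** The documents give no mean, SD or shape for percent change, so each figure here is conditional on an assumption. The shift was set so that one threshold yields 83% and 20%. For a normal shape this is z(0.83) − z(0.20) = 0.954 + 0.842 = 1.80 SD. Simulated two-sided power of the exact Wilcoxon rank-sum test at 5 versus 30:

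| Assumption | Power |
|---|---|
| Normal, equal SD | 0.925 |
| Logistic | 0.89 |
| t with 3 df | 0.83 |
| BRCA-positive SD 0.67, 1.5 or 2 times the other | 0.94, 0.89, 0.86 |
| BRCA changes only the responder category | 0.67 |
| Normal, 5% of patients unscanned and ranked worst | 0.82 |
| Normal, 10% of patients unscanned and ranked worst | 0.75 |

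The first four rows assume that every patient has a usable scan. The last row, and the case in which BRCA changes only the responder category, lie below Fisher's 0.788.

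**The case against.** The plan contains no error here. Fisher's test is standard and valid, the stated power is right, the text concedes that only large differences can be detected, and the analysis is exploratory. A gain of 4 to 6 points at the plan's rates may look like a matter of taste. All of this stands, and it is why the point is minor. It does not justify keeping the weaker test, because the replacement needs no distributional assumption and leaves the endpoint unchanged.

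A reader might go further and infer that the BRCA test should move to percent change in the target-lesion sum, since that sum is measured anyway and a rank test would reach about 93%. The documents do not support this:

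- The 93% needs an equal-variance normal shift and a usable scan from every patient, and the documents supply neither.
- Sections 13.2 and 13.4.2 count everyone who received one dose, so some analysed patients may have no percent change. No rate of missing scans is given, and at 10% the advantage has gone.
- Objective 5 concerns response. Under Section 11.1.4.4 response also depends on confirmation, non-target lesions and new lesions, so a patient can shrink past the 30% cut without being a confirmed responder. The powers of the two tests are therefore not powers for the same hypothesis.

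**Conclusion.** The concern holds as a small improvement to the test for objective 5. At 5 versus 30 and nominal two-sided 0.05, Fisher's test has a true size of at most 0.029 and power 0.788. Boschloo's test, ordered by the two-sided Fisher p-value, has a maximum size of 0.043 and power 0.844. The gain is 5.6 points at 5 versus 30, 4.2 points at 6 versus 29, and about 8 points if the BRCA-positive rate is 68%. These results rest on the plan's response rates and group split, and on the assumed level and sidedness.

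The rank test on percent change is worth adding only as support. No 93% figure should be claimed for it, and it should not displace the response test. Nor does the BRCA calculation carry over to the p53 correlation in objective 3. Section 9.1 names no test for p53, and a 60–80% deficiency rate (Section 2.4) would give a quite different group split, for which no power was worked out.

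**What to change.** In Section 9.1, keep the table of RECIST response by BRCA status. Replace Fisher's test with Boschloo's unconditional exact test at two-sided 0.05, with tables ordered by the two-sided Fisher p-value and the p-value maximised over the common response rate. Restate the power as 84% for 5 versus 30 (89% for 6 versus 29).

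Add one sentence for a supportive analysis: an exact Wilcoxon rank-sum test on best percent change from baseline in the target-lesion sum, with the worst rank for patients who have no post-baseline scan. Say that it is read alongside the response table and that the response test is the one that addresses objective 5.

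The cost is two or three sentences and slightly more analysis code. No new data, patients or visits are needed. The analysis stays exploratory, and the primary response endpoint and two-stage rule do not change.

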9.2 Laboratory Correlative Studies

Table 9-1 Biomarker sample collection schedule

Sample Specimen		Visit		
FFPE Archival Tumor	Tumor	Screening		
Research Biopsy	Tumor	Cycle 1 Day 1, 5-48hrs after Cisplatin Administration and Cycle 2 day 3, 5-8hrs (+/-24hrs) after AZD1775 administration		
cfDNA	Blood (EDTA-purple top)	Cycle 1 Day 1 Restaging visits Time of Progression		

9.2.1 Circulating cell free DNA Collection

Blood will be collected at baseline, restaging visits and at time of progression for evaluation of cell-free DNA (cfDNA). The cfDNA will be processed and banked in the DF/HCC Clinical Trials Core laboratory for future research purposes. The banked samples will be used to analyze DNA, RNA and protein in future studies.

After shipment to and storage within the DF/HCC Breast Bank, cfDNA plasma samples will be sent to the Broad Institute of MIT by the DFCI study team, under the care of [name], for sequencing. Using standard lab software, the Broad Institute will create randomly generated barcode labels with a sample number. The DFCI study team will label the plasma specimens with the labels provided and complete an Excel spreadsheet that correlates the barcode label with the patient's study ID and the timepoint of the sample. All samples will be de-identified and the Broad Institute, [name], and his staff, will not, in any way, be able to determine the identity of the patient.

9.2.1.1 Collection of Specimen(s)

20 ml of whole blood will be collected into 2 EDTA-containing purple top tubes. The blood sample will be collected and processed at baseline, restaging visits and time of progression for evaluation of cfDNA. Fill the tubes completely and immediately mix by gentle inversion 8 to 10 times. Inadequate or delayed mixing may result in accurate results. The banked samples will be used to analyze DNA, RNA and protein in future

studies.

9.2.1.2 Handling of Specimens(s)

20 ml of whole blood will be collected into 2 EDTA-containing purple top tubes. The blood sample will be collected and processed at baseline, restaging visits and time of progression for evaluation of cfDNA. Fill the tubes completely and immediately mix by gentle inversion 8 to 10 times. Inadequate or delayed mixing may result in accurate results.

9.2.2 Archival Tissue Collection

Formalin-fixed, paraffin-embedded (FFPE) biopsy specimens will be subjected to immunohistochemical analyses using standard procedures for: (1) Total CDC2; (2) phospho-CDC2; (3) gamma-H2AX; (4) phospho-Histone 3; and (5) cleaved caspase 3 and other relevant markers.

9.2.2.1 Collection of Specimen(s)

Formalin-fixed, paraffin-embedded (FFPE) or 15 unstained slides will be collected from participants archival tissue.

9.2.2.3 Site(s) Performing Correlative Study DFCI/BWH

9.2.3 **Biopsy Collection**

The study will obtain paired tumor biopsies for all patients enrolled with accessible disease (after cisplatin monotherapy and after cisplatin + AZD1775 combination therapy). Paired biopsies will be used to evaluate changes in pCDC2, gamma-H2AX, phsopho-Histone 3, and cleaved caspase 3 and other relevant markers. Additionally, the biopsies will be subjected to whole exome sequencing (WES) to capture BRCA reversion mutations (and the mutation status of most genes involved with double strange break repair), evidence of telometric allelic imbalance, and overall mutational signature.

After shipment to and storage within the DF/HCC Breast Bank, a portion of the paired biopsy samples will be sent to the Broad Institute of MIT by the DFCI study team, under the care of [name] [name]. Using standard lab software, the Broad Institute will create randomly generated barcode labels with a sample number. The DFCI study team will label the biopsy specimens with the labels provided and complete an Excel spreadsheet that correlates the barcode label with the patient's study ID and the timepoint of the sample. All samples will be de-identified and the Broad Institute, [name], and his staff, will not, in any way, be able to determine the identity of the patient.

9.2.3.1 Scheduling and Feasibility of Research Biopsies

The treating investigator will indicate the best lesion to target for potential biopsy, which will be ordered and scheduled per DFCI or BWH's institutional guidelines.

For research biopsies that are performed in the Cross-Sectional Interventional Radiology (CSIR) department, it will be expected that biopsy feasibility be reviewed within 24 hours of the scheduled procedure. If the radiologist determines that the selected area is unsafe or inappropriate in any way, the Radiologist will page the ordering provider to discuss the best course of action.

As biopsies for this trial may be occurring for research purposes only, with no additional clinical benefit to subjects, the threshold for determining safety and feasibility of the procedure must be lower than what might typically be used in determining safety and feasibility of a biopsy for clinical purposes. For this reason, the ordering provider will include information in the biopsy order comments that indicates that these biopsies are being performed for research purposes only and that the radiologist must use their best clinical judgement to determine if the procedure is unsafe. If at any point, a radiologist questions the safety of the procedure in question, they should not proceed.

9.2.3.2 Collection of Specimen(s)

Biopsies will be collected at C1D1 5-48hrs after Cisplatin administration and at C2D3 within 5-8hrs (+/- 24hrs) after the last dose of AZD1775 administration. If dosing is delayed placing the biopsy outside of the allowable window, the biopsy should be rescheduled to be within the window. If not feasible, the biopsy should be obtained as close to within the window as possible.

Tissue specimens will be collected from recurrent or metastatic lesions using standard institutional procedures. The amount of tissue collected will follow the guidelines listed below. If a participant has more than one site of disease, only one site needs to be biopsied in order to go on to the study and the site is left to the discretion of the patient and their treating physician. Fine need aspirates (FNA) is not allowed. Participants who undergo a research biopsy procedure for the purpose of this protocol, and in whom inadequatetissue is obtained, are still eligible and are not required to undergo a repeat biopsy in order to enter the study.

Breast: A goal of 3-6 core biopsy specimens will be obtained using standard institutional guidelines for a diagnostic core biopsy of a breast mass.

Skin/chest wall: A goal of 1-2 5-mm punch biopsies will be obtained.

Lymph node: A goal of 3-6 core biopsy specimens will be obtained using an 18-gauge needle.

Liver: A goal of 3-6 core biopsy specimens will be obtained using an 18-gauge needle.

Lung: Because of the risk of pneumothorax associated with core needle biopsies of lung nodules, no core biopsies of lung nodules will be performed on this protocol, unless they are clinically indicated.

Bone: Because the yield of malignant tissue from bone biopsies tends to be relatively low, if a participant has another accessible site of disease (i.e. skin, lymph node, liver), that site should be biopsied preferentially. If bone is the only biopsy-accessible site, then a goal of 3-6 core biopsy specimens will be obtained using an 11-13gauge needle.

Pleural Fluid: A goal of 500 cc of pleural fluid will be obtained with a standard thoracentesis procedure, with or without image guidance, according to the clinical judgment of the treating physician and clinician performing the procedure. Less than the goal amount is acceptable, and should be based upon the clinical judgment of the Investigator and the clinician performing the procedure. If more than the goal amount of fluid is obtained, then the entire specimen (with the exception of what is needed for clinical purposes, if applicable) will be stored in the tissue bank.

Ascites fluid: A goal of 500 cc of ascites fluid will be obtained with a standard paracentesis procedure, with or without image guidance, according to the clinical judgment of the treating physician and clinician performing the procedure. Less than the goal amount is acceptable, and should be based upon the clinical judgment of the Investigator and the clinician performing the procedure. If more than the goal amount of fluid is obtained, then the entire specimen (with the exception of what is needed for clinical purposes, if applicable) will be stored in the tissue bank.

Please note that the above are guidelines for the amount of tissue to be obtained at the baseline biopsy, and are not meant to replace clinical judgment at the time the procedure is performed. Less than the goal quantity of tissue is accepted for each type of biopsy, and will be left to the clinical judgment of the physician performing the procedure. If ascites or pleural fluid is to be used as the investigational biopsy specimen, consideration should be given to confirming the malignant nature of the ascites or pleural fluid prior to study entry.

If a patient is undergoing resection of a lesion for clinical reasons (i.e. wedge resection of a new lung lesion for confirmation of diagnosis or re-testing of hormone receptor or HER2 status; or, resection of a chest wall lesion; or, resection of a lymph node), then the patient may opt to have a portion of that tissue stored for research at the time of the procedure (provided that the tissue is processed as specified in Section 9.2.1.2), in which case, the participant would not be required to undergo a separate research biopsy for entry into this protocol.

9.2.3.3 Handling of Specimens(s)

Core biopsy specimens will be handled and processed at the time of biopsy collection. Ideally, sufficient core biopsy samples will be obtained to allow for some to be frozen (after embeding in OCT) and others to be fixed in formalin and subsequently embedded into paraffin blocks. The specific instructions for handling core biopsy material is provided in Appendix C.

9.2.3.5 Site(s) Performing Correlative Study

Dana-Farber Cancer Institute

9.2.3.6 Risks of Research Biopsy and Procedures for Minimizing Risk

Potential risks according to site are:

Breast (core biopsy):

- Likely: local discomfort and minor bleeding.
- Less likely: moderate or major bleeding, need for blood transfusion, hospitalization due to bleeding or other complications, infection, pneumothorax, damage to adjacent organs.

Skin/chest wall (punch biopsy):

- Likely: local discomfort and minor bleeding
- Less likely: moderate or major bleeding, or infection

Lymph node, liver, or bone (core needle biopsy):

- Likely: local discomfort and minor bleeding
- Less likely: moderate or major bleeding, need for blood transfusion, hospitalization due to bleeding or other complications, infection, damage to adjacent organs. Additional risks may be present if

intravenous conscious sedation is required

Pleural fluid (thoracentesis):

- Likely: local discomfort and minor bleeding
- Less likely: moderate or major bleeding, need for blood transfusion, hospitalization due to bleeding or other complications, infection, pneumothorax, damage to adjacent organs

Ascites fluid (paracentesis):

- Likely: local discomfort and minor bleeding
- Less likely: moderate or major bleeding, need for blood transfusion, hospitalization due to bleeding or other complications, infection, bowel perforation or damage to adjacent organs. In order to minimize the risk of a biopsy, only qualified personnel will perform these procedures.

Prior to the procedure, the physician performing the procedure will discuss the risks with each study participant, answer any questions, and obtain separate procedure consent. Patients will be evaluated for comorbidities or concomitant medications that may increase the risk of potential complications. For biopsies of lesions that are not superficial and clearly palpable, imaging studies such as CT or ultrasound will be used to guide the biopsy in order to minimize the risk of damage to adjacent structures. After lymph node biopsies, patients will be observed a minimum of 2 hours (range 2-4 hours) after the procedure, or according to standard institutional guidelines. After liver biopsies, patients will be observed a minimum of 4 hours (range 4-6 hours) after the procedure, or according to standard institutional guidelines. Less than the goal quantity of tissue is accepted for each type of biopsy, and will be left to the clinical judgment of the physician performing the procedure.

